9.7.3 SAFETY

The safety population is defined as all subjects who enrolled and received at least 1 dose of study drug. The safety population will be analyzed by treatment dose the subject received rather than the treatment dose selected for the subject by the Investigator. The safety analysis set will be used to conduct safety analyses.

Demographic and baseline characteristics will be summarized for the ITT, PP, and safety populations.

9.13 PROTOCOL DEVIATIONS

Subjects with major protocol deviations will be excluded from the PP population. Protocol deviations will be summarized for all enrolled subjects. A data listing will be provided by subject.

10 SUPPORTING DOCUMENTATION AND OPERATIONAL CONSIDERATIONS

10.1 REGULATORY, ETHICAL, AND STUDY OVERSIGHT CONSIDERATIONS

10.1.1 INFORMED CONSENT PROCESS

10.1.1.1 CONSENT/ASSENT AND OTHER INFORMATIONAL DOCUMENTS PROVIDED TO PARTICIPANTS

[figure not shown]
Consent forms describing in detail the study intervention, study procedures, and risks are given to the participant and written documentation of informed consent is required prior to starting intervention/administering study intervention.

[figure not shown]
10.1.1.2 CONSENT PROCEDURES AND DOCUMENTATION

Informed consent is a process that is initiated prior to the individual's agreeing to participate in the study and continues throughout the individual's study participation. Written informed consent will be obtained from all subjects before any study-related procedures (including any pre-treatment screening procedures) are performed. The investigator may discuss the study and the possibility for entry with a potential subject without first obtaining consent. However, a subject wishing to participate must give written informed consent prior to any study-related procedures being conducted, including those performed solely for the purpose of determining eligibility for study participation, and including withdrawal from current medication (if required prior to study entry). The investigator has both the ethical and legal responsibility to ensure that each subject being considered for inclusion in this study has been given a full explanation of the procedures and expectations for study participation.

When applicable, the site-specific informed consent must be forwarded to the sponsor for approval prior to submission to an IRB/REB/EC that is registered with appropriate local or federal agencies as required. Each subject will sign the consent form that has been approved by the same IRB/REB/EC that was responsible for protocol approval. Each informed consent document must adhere to the ethical principles stated in the Declaration of Helsinki and will include the elements required by FDA regulations in 21 CFR Part 50, Health Canada's Food and Drug Regulations, Division 5, European Medicines Agency (EMA), as well as the elements required by the International Council on Harmonisation (ICH) Good Clinical Practice (GCP) guideline, and applicable national and local regulatory requirements. The consent form must also include a statement that the sponsor, their designees, and auditing regulatory agencies will have direct access to the subject's records and medical history for study related purposes.

Once the appropriate essential information has been provided to the subject and fully explained by the investigator (or a qualified designee) and it is felt that the subject understands the implications and risks of participating in the study, the IRB/REB/EC approved consent document shall be signed and dated by both the subject and the person obtaining consent (investigator or designee), and by any other parties required by the IRB/REB/EC or other Regulatory Authorities. The subject will be given a copy of the

10.1.6 SAFETY OVERSIGHT

Safety oversight will be under the direction of an independent Data Monitoring Committee/Data Safety Monitoring Board (DMC/DSMB) composed of individuals with the appropriate expertise, including indication and/or neuromodulators and/or data management. The DMC/DSMB will be appointed to review safety data during the study and will monitor quality and completeness of the safety data, as well as signals and outcomes (SAEs, AEs, laboratories, and other outcome data). Data will be reviewed unblinded, as this is an open label study.

The DMC/DSMB will consist of 5 members, including a chair, a biostatistician, two neurologists, and a pulmonologist. Details of the composition, identity of members, and scope of the committee's mandate will be presented in a DMC/DSMB charter document.

10.1.7 CLINICAL MONITORING

All aspects of the study will be monitored by the sponsor or authorized representatives of the sponsor according to GCP and Standard Operating Procedures (SOPs) for compliance with applicable government regulations, (i.e., Informed Consent Regulations [US 21CFR, Part 50] and Institutional Review Board regulations [US 21CFR, Part 56.103]). [REDACTED]

[REDACTED]

[REDACTED]

[REDACTED]

[REDACTED]

[REDACTED]

[REDACTED]

[REDACTED]

[REDACTED]

[REDACTED]

[REDACTED]

10.1.9 DATA HANDLING AND RECORD KEEPING

10.1.9.1 DATA COLLECTION AND MANAGEMENT RESPONSIBILITIES

For this study, all protocol-specified data will be recorded in the source documents, and data will be entered on the eCRFs from the source documents. In addition to signature confirmation that a subject meets the study eligibility criteria, upon each subject's completion of the study, the investigator will sign a statement indicating that all pages of the subject's case report have been reviewed. Signature stamps and "per signatures" are not acceptable.

It is sponsor's policy that the study data be verifiable with the source data that necessitates access to all original recordings, laboratory reports, and other records for each subject. The investigator must therefore agree to allow access to subjects' records, and source data must be made available for all study data. Subjects (or their legal representatives) must also allow access to their medical records. Subjects will be informed of the importance of increased record access and permission granted by signature on the informed consent document prior to Screening.

Checks will be performed to ensure the quality, consistency, and completeness of the data. Instances of missing or uninterpretable data will be resolved with the investigator or study coordinator. Data queries, documented on data query forms, will be sent to the research facility. Site personnel will be responsible for providing resolutions to the data queries and for correcting the eCRFs, as appropriate. All unused sponsor source documents and binders must be returned to the sponsor upon completion of the study.

The investigator must keep written or electronic source documents for every subject participating in the clinical study. The subject file that identifies the study in which the subject is participating must include the subject's available demographic and medical information including:

- Name

- Contact information
- Age
- Sex
- Medical history
- Concomitant diseases
- Concomitant therapies/medication
- Study visit dates
- Performed examinations, evaluations, and clinical findings
- Investigational product administration
- AEs, SAEs, or pregnancy (as applicable)

Additionally, any other documents with source data, especially original printouts of data that were generated by technical equipment must be included in the subject's source document (e.g., laboratory value listings). All these documents must have at least the subject's study number, and the date of the evaluation.

The data recorded during the course of the study will be documented in the eCRF and/or the study-specific forms. Before or at study termination, all data must be forwarded to the sponsor. The data will then be recorded, evaluated, and stored in anonymous or coded form in accordance with data-protection regulations.

Subjects will authorize the use of their protected health information during the informed consent process in accordance with the applicable privacy requirements. Subjects who deny permission to use and disclose protected health information will not be eligible to participate in the study. The investigator will ensure that the study documents forwarded to the sponsor, and any other documents, contain no mention of subject names.

Any amendments and corrections necessary will be undertaken in both the source documents and eCRFs (as appropriate) and countersigned by the investigator, or documented designee, stating the date of the amendment/correction. Errors must remain legible and may not be deleted with correction aids. The investigator must state his/her reason for the correction of any data. In the case of missing data/remarks, the entry spaces provided in the eCRF should be cancelled out so as to avoid unnecessary follow-up inquiries.

Regulatory authorities, the IRB/REB/EC and/or the sponsor's Quality Assurance group (or designee) may request access to all source documents, eCRFs, and other study documentation for on-site audit or inspection. The investigator must guarantee direct access to these documents. Electronic CRFs (eCRFs) will be kept by the sponsor or an authorized designee in a secured area. Clinical data will be recorded in a computer format for subsequent statistical analyses. Data files will be stored on electronic media with a final master data file kept by the sponsor after descriptive and statistical analyses and reports have been generated and are complete.

It is the responsibility of the investigator to ensure that the study center file is maintained in accordance with the ICH Guidance for Industry E6 Good Clinical Practice: Consolidated Guidance, Section 8 – Essential Documents for the Conduct of a Clinical Trial.

10.1.9.2 STUDY RECORDS RETENTION

It is a sponsor requirement that all investigators participating in clinical studies maintain detailed clinical data for one of the following periods:

- Country-specific requirements, or
- A period of at least two years following the last approval of a marketing application approved by a Regulatory Authority in an ICH region or until there are no pending or contemplated marketing applications in an ICH region, or
- A period of two years after the sponsor notifies the investigator that the data will not be submitted for review by any Regulatory Authority

The investigator must not dispose of any records or essential documents relevant to this study without either (1) written permission from the sponsor, or (2) providing an opportunity for the sponsor to collect such records. The investigator shall take responsibility for maintaining adequate and accurate electronic or hard copy source documents of all observations and data generated during this study. Such documentation is subject to inspection by the sponsor and relevant regulatory agencies. If the investigator withdraws from the study (e.g., relocation, retirement) all study-related records should be transferred to a mutually agreed upon designee. Notice of such transfer will be provided to sponsor in writing.

10.1.9.3 TREATMENT OF MISSING DATA

Some data elements will be missing in this study due to subjects who withdraw from the study, subjects who are lost to follow-up, or subjects who do not complete all study visits. The completion status of each subject will be documented (e.g., completed protocol, withdrew from study, lost to follow-up, etc.). All reasonable efforts will be made by the study staff to maintain contact with the study participants during their participation in the study. The study coordinator will attempt to contact any subjects who are lost to follow-up. For subjects who are unwilling to return to clinic for follow-up, the study coordinator will attempt to contact them and to collect study data from them during a telephone call or by forms sent to them through the mail.

[figure not shown]
10.1.9.4 PROTOCOL DEVIATIONS

A protocol deviation is any noncompliance with the clinical trial protocol. The noncompliance may be either on the part of the participant, the investigator, or the study site staff. As a result of deviations, corrective actions are to be developed by the site and implemented promptly.

It is the responsibility of the site investigator to use continuous vigilance to identify and report deviations as soon as possible. All deviations must be addressed in study source documents and must be sent to the reviewing IRB/REB/EC per their policies. The site investigator is responsible for knowing and adhering to the reviewing IRB/REB/EC requirements.

This study will be conducted as described in this protocol, except for an emergency situation in which the protection, safety, and well-being of the subject requires immediate intervention, based on the judgment of the investigator (or a responsible, appropriately trained professional designated by the investigator). In the event of a significant deviation from the protocol due to an emergency, accident, or mistake, the investigator or designee must contact the medical monitor and the sponsor at the earliest possible time by

[figure not shown]
telephone. This will allow an early joint decision regarding the subject's continuation in the study. This decision will be documented by the investigator and the medical monitor.

[figure not shown]

[figure not shown]
10.2 ADDITIONAL CONSIDERATIONS

[figure not shown]
10.2.1 ETHICS AND RESPONSIBILITY

[figure not shown]
This study must be conducted in compliance with the protocol, the ICH Guidance for Industry E6 Good Clinical Practice: Consolidated Guidance, the Declaration of Helsinki, IRB, REB, or EC requirements and all applicable national and local regulatory requirements. Investigators must submit all essential regulatory documentation, as required by local and national regulations (including approval of the protocol and informed consent form by an HHS-registered IRB/REB/EC) to the sponsor before investigational product will be shipped to the study site.

[figure not shown]

[figure not shown]

[figure not shown]

[figure not shown]

[figure not shown]
*UNILATERAL injection only

[figure not shown]

[figure not shown]

[figure not shown]

[figure not shown]

SF-36[®] Health Survey © 1992, 1996, 2000 Medical Outcomes Trust and QualityMetric Incorporated. All rights reserved.
SF-36[®] is a registered trademark of Medical Outcomes Trust.
(SF-36v2[®] Health Survey Standard, United States (English))

The purpose of this statistical analysis plan (SAP) is to ensure that the data listings, summary tables and figures which will be produced, and the statistical methodologies that will be used, are complete and appropriate to allow valid conclusions regarding the study objectives.

2.1. Responsibilities

Syneos Health will perform the statistical analyses and are responsible for the production and quality control of all tables, figures and listings.

2.2. Timings of Analyses

The primary analysis is planned after all subjects complete the final study visit or terminate early from the study.

An independent Data Safety Monitoring Board (DSMB) will review descriptive summaries of accumulating safety data during the study and will monitor quality and completeness of the safety data, as well as signals and outcomes of the safety data. Further description of the DSMB analyses and timing of the analyses can be found in the DSMB charter Version 1.0 10-July-2018.

This document is confidential.

3. Study Objectives

3.1. Primary Objectives

The primary objectives of this study are to evaluate the long-term safety of multiple continuous treatments of daxibotulinumtoxinA (DAXI) for injection, and to assess immunogenicity of BoNTA and RTP004 after multiple treatments of DAXI for injection in adults with isolated cervical dystonia (CD).

[REDACTED]

[REDACTED]

3.4. Brief Description

This is a Phase 3, open-label, multi-center trial to evaluate the long-term safety, efficacy, and immunogenicity of up to four continuous treatment cycles of DAXI for injection at doses of 125 U, 200 U, 250 U, and 300 U in adults with isolated CD at study centers across the United States, Canada, and Europe.

Approximately 350 adult subjects will be recruited from study centers who were previously enrolled in Protocol 1720302 entitled [A Phase 3, Randomized, Double-Blind, Placebo-Controlled, Parallel Group, Multi-Center Trial to Evaluate the Efficacy and Safety of a Single Treatment of DaxibotulinumtoxinA for Injection in Adults with Isolated Cervical Dystonia (ASPEN-1)]. These subjects will have 7 days from their End-of-Study (EOS) Visit in Protocol 1720302 to decide if they want to enroll in this study. After enrolling, subjects will have up to 21 days to complete screening procedures. After 21 days, subjects who have NOT completed the screening procedures will be considered a screen failure. To be reconsidered for enrollment to this study, the subject will be required to repeat all screening procedures to reconfirm eligibility for enrollment. These criteria also apply to subjects who missed the 7-day decision-making window to enroll in this study. This study will also recruit new botulinum neurotoxin (BoNT) treatment-naïve or -experienced adult subjects who were not enrolled in Protocol 1720302.

[REDACTED]

[REDACTED]

This document is confidential.

[REDACTED]

The primary endpoints are safety and immunogenicity. [REDACTED]

[REDACTED]

3.5. Subject Selection

3.5.1. Inclusion Criteria

All participants must meet the following inclusion criteria:

1. Adults, 18 to 80 years of age
2. Meets diagnostic criteria for isolated CD (idiopathic; dystonic symptoms localized to the head, neck, shoulder areas) with at least moderate severity at Baseline (Day 1), defined as a TWSTRS total score of at least 20 with at least 15 on the TWSTRS Severity subscale and at least 3 on the TWSTRS Disability subscale, and at least 1 on the TWSTRS Pain subscale (minimum subscale criteria applicable only to subjects not previously enrolled in Study Protocol 1720302)
3. Subjects who were previously enrolled in Protocol 1720302, who completed the study, including:
 - a. Those with no reduction or have an increase from baseline in the average TWSTRS total score at Weeks 4 and 6 (i.e., no improvement or worsened disease status), and the investigator agreed that there was a need for retreatment based on the subject's symptoms and neurologic examination findings.
 - b. Those who benefited from study treatment and complete follow-up visits up to the time point of when their TWSTRS total score reached/exceeded their target TWSTRS score
 - c. Those who benefit from study treatment but subsequently experienced significant recurrence of CD symptoms (e.g., pain) during the study before their TWSTRS total score reached their target based on the subject's symptoms and neurological exam findings
 - d. Those who completed study visits up to Week 36 and their TWSTRS total score never reached their target TWSTRS score and they never requested another retreatment. The investigator determine that these subjects can be followed in this study until their TWSTRS total score is the same or higher than their target TWSTRS score or until they request retreatment, which the investigator determined is clinically indicated
4. De novo subjects (not previously enrolled in Protocol 1720302):
 - a. Naïve to BoNT treatment
 - b. BoNT treatment-experienced: if previously treated with BoNTA, the subject must have demonstrated a clinically meaningful response to the last BoNTA treatment based on the clinical judgment of the investigator

This document is confidential.

5. Written informed consent including authorization to release health information

3.5.2. Exclusion Criteria

Subjects will not be enrolled if they meet any of the following exclusion criteria:

1. CD attributable to an underlying etiology, (e.g., trauma torticollis or tardive torticollis)
2. Predominant retrocollis or anterocollis CD
3. Significant dystonia in other body areas, or is currently being treated with BoNT for dystonia in areas other than those associated with isolated CD
4. Severe dysphagia (Grade 3 or 4 on the Dysphagia Severity Scale) at Screening or Baseline (prior to study treatment)

[REDACTED]

[REDACTED]

[REDACTED]

[REDACTED]

[REDACTED]

[REDACTED]

[REDACTED]

[REDACTED]

[REDACTED]

This document is confidential.

[REDACTED]

[REDACTED]

[REDACTED]

[REDACTED]

[REDACTED]

[REDACTED]

[REDACTED]

[REDACTED]

[REDACTED]

[REDACTED]

[REDACTED]

No additional exclusions may be applied by the investigator, in order to ensure that the study population will be representative of all eligible subjects. Deviation from any entry criterion excludes a subject from enrollment into the study.

3.6. Determination of Sample Size

The sample size for this study is based on a requirement from Regulatory Authorities to collect safety data on approximately 350 subjects treated once and long-term safety data on at least 100 adult subjects with isolated CD treated with 3 or 4 continuous treatment cycles, of low-dose or high-dose DAXI for injection, with at least 50 subjects treated with the high-dose DAXI for injection for 3 or 4 continuous treatment cycles. [REDACTED]

This document is confidential.

[REDACTED]

[REDACTED]

[REDACTED]

[REDACTED]

[REDACTED]

[REDACTED]

[REDACTED]

[REDACTED]

[figure not shown]
[REDACTED]

[figure not shown]
[REDACTED]

3.9. [REDACTED]

[REDACTED]

This document is confidential.

[figure not shown]

4. Endpoints

4.1. Primary Endpoints

The primary endpoints of this study are:

- The dose- and cycle-specific incidence of drug-related adverse events (AEs)
- The dose- and cycle-specific incidence of study drug discontinuation due to drug-related AEs
- The dose- and cycle-specific incidence of treatment-emergent immunogenicity

This document is confidential.

5. Analysis Sets

5.1. Screened Population

The Screened Population includes all subjects screened for entry into the study. This population will be used for disposition summaries and listings.

5.2. Enrolled Population

The Enrolled Population includes all subjects enrolled into the study. This population will be used for protocol deviation summaries and all listings.

5.3. Safety Population

The safety population is defined as all subjects who enrolled and received at least 1 dose of study drug. The safety population will be analyzed by treatment dose the subject received rather than the treatment dose selected for the subject by the Investigator. The safety analysis set will be used for all analyses

5.4. Non-COVID-19 Impacted Analysis Set

The non-COVID-19 impacted population is a subset of the safety population and excludes assessments with any COVID-19 related protocol deviations. [REDACTED]

5.5. Protocol Deviations

Protocol deviations will be summarized for all enrolled subjects. COVID-19 related deviations will be identified when collecting protocol deviations. They will be summarized separately and will include number of subjects impacted, as well as missed visits, missed assessments, remote visits, and remote assessments. A listing will be provided for all protocol deviations. A separate listing will be provided for all COVID-19 related protocol deviations.

This document is confidential.

6. General Aspects for Statistical Analysis

6.1. General Methods

- Efficacy endpoints will be summarized by dose and/or treatment cycle, unless otherwise specified.
- Continuous variables will be summarized using the number of observations (n), mean, standard deviation (SD), median, minimum (min), and maximum (max). Categorical variables will be summarized using number of observations (n), frequency and percentages of subjects.
- All relevant subject data will be included in listings. All subjects entered into the database will be included in subject data listings.
- Unless otherwise specified, if a subject has more than one observation at a given time point, the value closest to the target day for that visit will be used. If two observations are equal distance from the target day, the later observation will be used.
- All analyses and outputs will be generated using SAS® version 9.4 or higher.

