8.1.3 VARIATION FROM SCHEDULED VISIT DAYS

To allow for scheduling flexibility, limited variation will be permitted from the specified time of each visit (Table 3).

Table 3. Allowed Variation from Scheduled Visit Days

Scheduled Visit After Each Treatment	Allowed Variation (calendar days)
Weeks 4 and 6	± 3 days
Weeks 12, 16, 20, 24, 28, 32, 36, 40, 44, 48, and 52/EOS	± 6 days
Treatment #2, #3, and #4	± 14 days

Note: Two weeks after each Treatment (at Week 2 [allowed variation: ± 3 days]), the subject will be contacted by telephone to follow up on clinical effect, any AEs or changes in concomitant medications.

A subject who experiences significant recurrence of CD symptoms (e.g. pain) during the study before his/her TWSTRS-total score reaches the target TWSTRS score may request another treatment before the next scheduled visit. In this case, the subject may have an unscheduled visit for the investigator to assess whether another treatment is warranted based on the subject's symptoms and neurologic exam findings. If the investigator confirms that retreatment is clinically indicated, the subject may receive another treatment at this visit, unless less than 12 weeks have passed since the last injection or the injection will occur after Week 40 (i.e., there is less than 12 weeks of follow up left in the 52-week study period).

Note: After each Treatment, study visits are reset to begin from that Treatment to Week 4, Week 6, Week 12, and every 4 weeks thereafter.

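### The visible SAP reports the two AE-based primary incidences as numbers and percentages only, with no interval, although late dose-by-cycle cells may be small

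*SAP*

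**What the plan says.** SAP 3.4 describes "up to four continuous treatment cycles of DAXI for injection at doses of 125 U, 200 U, 250 U, and 300 U". SAP 4.1 defines all three primary endpoints by dose and cycle: the incidence of drug-related AEs, "The dose- and cycle-specific incidence of study drug discontinuation due to drug-related AEs", and "The dose- and cycle-specific incidence of treatment-emergent immunogenicity".

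The general reporting rule in SAP 6.1 is "Categorical variables will be summarized using number of observations (n), frequency and percentages of subjects". SAP 9.3 follows it. The tables of treatment-emergent AEs, including treatment-related events and events resulting in study medication discontinuation, are laid out by dose and cycle plus overall, and show number and percentage of subjects. The same section adds four pooled groups: high dose (250 or 300 U) or low dose (125 or 200 U), each for 3 or 4 cycles or for 1 or 2 cycles.

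The only confidence interval in the visible text of either document is for median duration of effect (Protocol 9.6).

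SAP 3.6 bases the size on exposure: "safety data on approximately 350 subjects treated once", at least 100 subjects with 3 or 4 cycles, "with at least 50 subjects treated with the high-dose DAXI for injection for 3 or 4 continuous treatment cycles". The text after that is redacted. SAP 5.3 indicates that the investigator selects the dose.

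**The concern.** The trial asks whether repeated treatment is safe. For uncommon events the useful answer is how high a rate the data can exclude, and that is an upper limit rather than a point estimate. Four doses by four cycles make up to 16 cells, while the visible exposure targets are set on pooled doses. A zero percentage in a late-cycle cell can then read as absence of risk, and differences between neighbouring cells can read as dose or cycle trends when they are noise. The plan gives an interval to an efficacy summary and, in its visible text, none to the primary safety incidences.

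**Working it through.** **The plan's own figure.** The size is a regulatory exposure requirement. No error rate, power or event rate is visible with it, so there is no calculation to reproduce. The check is what precision the stated counts would give.

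**Inputs.**
- Four doses and up to four cycles (SAP 3.4): 4 × 4 = 16 cells.
- About 350 subjects treated once; at least 100 with 3 or 4 cycles; at least 50 of these at high dose (SAP 3.6).
- High dose pools two dose levels (SAP 9.3).
- Assumption: equal split over doses. This gives 350/4 = 87.5, about 88 per dose in cycle 1; 100/4 = 25 per dose by cycle 3; and, within high dose, 50/2 = 25. The documents state no split.

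**Upper limit with no events.** The exact (Clopper-Pearson) two-sided 95% upper limit U solves (1 − U)^n = 0.025, so U = 1 − 0.025^(1/n).

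| n | What it represents | Upper limit for 0 events |
|---|---|---|
| 350 | all subjects treated once | 1.05% |
| 100 | minimum with 3 or 4 cycles, all doses | 3.6% |
| 88 | one dose in cycle 1, equal split | 4.1% |
| 50 | minimum with 3 or 4 cycles, high dose | 7.1% |
| 25 | one dose by cycle 3, equal split | 13.7% |
| 10 | smaller dose if 50 split 40 and 10 | 30.8% |
| 5 | smaller dose if 50 split 45 and 5 | 52.2% |

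The figure at n = 25 depends somewhat on the method: a one-sided 95% limit is 1 − 0.05^(1/25) = 11.3%, the rule of three gives 3/25 = 12.0%, and Wilson gives 13.3%.

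**Chance of an empty cell.** With 25 subjects and a true rate p, the chance of seeing no events is (1 − p)^25. For p = 5% this is 0.95^25 = 27.7%; for p = 10% it is 0.90^25 = 7.2%.

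**A non-zero cell.** For 2 events in 25 (8%), the exact two-sided 95% interval is 1.0% to 26.0%.

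**Cycle 4.** Protocol 8.1.3 does not allow retreatment at an unscheduled visit if fewer than 12 weeks have passed since the last injection, or if "the injection will occur after Week 40 (i.e., there is less than 12 weeks of follow up left in the 52-week study period"). Three earlier cycles of at least 12 weeks take 3 × 12 = 36 weeks, which leaves 40 − 36 = 4 weeks of slack across all three. How many subjects fit within that depends on the distribution of cycle lengths, which the documents do not give.

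**The case against.** The strongest reply is that the study is open-label and descriptive, no hypothesis test is visible, every table shows n, all AEs are listed, and any reader can derive an exact limit from the count and the denominator. That is fair: no planned analysis fails without intervals. But the primary tables are where readers will look for the precision, and it costs little to show it there.

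Pooling is also already planned. The overall column rests on far more subjects than a late cell, and the group with high dose for 3 or 4 cycles matches the high-dose exposure target. This stands, but these summaries show no interval either. The four groups are also not cycle-specific. They are defined by the number of cycles eventually received, and Protocol 7.1 lets significant adverse effects end treatment. Subjects who stop early for that reason therefore tend to fall in the 1-or-2-cycle groups.

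Three stronger readings are tempting, and the documents do not support them:
- **That the plan secures about 25 subjects per dose by cycle 3.** The minimums are pooled, and 25 is an equal-split average of a minimum. Doses are chosen by the investigator and SAP 9.3 provides for subjects who mix high and low doses, so a cell can be smaller. It can also be larger, because 100 and 50 are minimums.
- **That cycle 4 will hold only a handful of subjects per dose.** Counting scheduled visits alone suggests this, but Protocol 8.1.3 permits retreatment at unscheduled visits, so intervals such as 13 + 13 + 14 = 40 weeks also qualify. No figure follows from the documents.
- **That the immunogenicity incidence has no interval.** No analysis of it is visible, and SAP 9.4 and 9.6 are redacted, so this cannot be asserted.

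**Conclusion.** The point holds for the two AE-based primary endpoints as far as the text is visible: their incidences appear as number and percentage, without an interval, in the dose-by-cycle tables, the overall column and the pooled groups. It is a weakness of reporting that should be put right, not an error in design or data.

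Its size depends on the cell. Under an equal split of the 100-subject minimum, zero events in a cycle-3 dose cell leaves a rate of up to 13.7% not excluded (exact, two-sided 95%), and more in smaller cells. It does not apply equally everywhere: under the same split the cycle 1 limit is about 4.1%, and over all 350 subjects it is 1.05%. A minimum per dose, or a precision statement, may lie in the redacted text after the sample-size sentence. Cycle 4 has little slack in time, but its size cannot be computed.

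**What to change.** In SAP 6.1 and 9.3, report each AE-based primary incidence with its denominator and an exact Clopper-Pearson 95% confidence interval, counting each subject once per cycle in the cycle-specific tables. Do this in the dose-by-cycle tables, the overall column and the four pooled dose-frequency groups. Where no events are seen, quote the upper limit in the report.

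Add a supplementary table by cycle for low dose (125 and 200 U) and high dose (250 and 300 U) with the same intervals. It should stand beside the dose-by-cycle table and not replace it, since that table is what the protocol defines as primary.

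Apply the same to the immunogenicity incidence if the redacted section does not already do so.

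The cost is SAP wording and minor programming, with no new data. The drawback for the sponsor is that zero or low rates look less favourable once the upper limit stands next to them.
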